7.5.4. On-Treatment ALT Flare and Post-Treatment Exacerbation of Hepatitis B Management

In On-Treatment ALT Flare is defined as:

- Confirmed (within 3 days of receipt of initial laboratory results) serum ALT $> 2 \times$ Day 1 value and $>10 \times$ ULN, with or without associated symptoms.

7.5.4.1. Management of ALT Flare in Subjects Receiving Study Medication

If laboratory results indicate elevation of ALT $> 2 \times$ Day 1 value and $> 10 \times$ ULN, the following is recommended:

- Schedule the subject to return to the clinic as soon as possible (ideally within 3 days after initial laboratory results were drawn). During the visit, a clinical assessment of the subject will be performed. The assessment should include a physical examination and evaluation of the subject's mental status.
- If the ALT elevation is confirmed, request the central clinical laboratory to conduct reflex testing for PT/INR, plasma HBV DNA, HBV serology (HBsAg, HBsAb, HBeAg and HBeAb), HDV, HAV IgM, and HCV serology
- Check the following laboratory parameters: serum ALT and AST, total bilirubin, INR, and serum albumin. Based on the results of the confirmatory tests, the following treatment modifications are recommended.

Elevated Liver Enzymes, Normal or Stable relative to Day 1 Liver Function Tests

If ALT levels are elevated (ie, $> 2 \times$ Day 1 and $> 10 \times$ ULN) with normal or stable total bilirubin and INR relative to Day 1, the subject may remain on study medication and should be monitored weekly as long as ALT levels return to normal or Day 1 level. During monitoring, if the ALT values remain persistently elevated, the Investigator should discuss with the Gilead Medical Monitor whether the study drug should be discontinued.

Elevated Liver Enzymes, Elevated Liver Function Tests

If ALT values are elevated (ie, $> 2 \times$ Day 1 and $> 10 \times$ ULN), and total bilirubin is confirmed to be 2 x Day 1 value, and INR is 0.5 above Day 1, provided both are $> ULN$, the investigator should consider discontinuing study medication (upon discussion with the Gilead Medical Monitor, unless the safety of the patient is of immediate concern). The subject should be monitored weekly as long as ALT, total bilirubin, and INR values remain elevated or above Day 1 values.

During monitoring, if the ALT values and the liver function tests remain persistently elevated, the Investigator should discuss with the Gilead Medical Monitor whether the study drug should be discontinued.

7.5.4.2. Management of Exacerbation of Hepatitis B in Subjects who have Discontinued Study Medication

If laboratory results indicate (1) an ALT elevation $> 2 \times$ Day 1 and $> 10 \times$ ULN alone OR associated with (2) abnormal laboratory parameters suggestive of worsening hepatic function (total bilirubin $2 \times$ Day 1, INR 0.5 above Day 1, provided both are $> ULN$) and the subject is on no post-study therapy for HBV, the following is recommended:

- Schedule the subject to return to the clinic as soon as possible (ideally no later than 3 days after the initial laboratory values were drawn). During the visit, perform a clinical assessment of the subject.
- Check the following laboratory parameters: serum ALT and AST, bilirubin, INR, and albumin.
- If the ALT elevation is confirmed, request the clinical laboratory to conduct reflex testing for plasma HBV DNA, HBV serology (HBsAg, HBsAb, HBeAg, HBeAb), HDV, HAV IgM and HCV. If plasma HBV DNA is increasing, the investigator should consider immediate initiation of approved therapy.
- The subject should be followed until laboratory parameters (ALT, total bilirubin, INR) return to normal or Day 1 up to a maximum of 6 months after the initial occurrence of the event.

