1.6. Risk/Benefit Assessment for the Study

HIV and HBV co-infection worsens morbidity and mortality synergistically; co-infected patients have higher risk of cirrhosis and hepatocellular carcinoma. In HIV-positive patients co-infected with HBV, F/TDF or F/TAF are the preferred NRTI backbone of a fully suppressive antiretroviral regimen {[Panel on Antiretroviral Guidelines for Adults and Adolescents 2016](#)}. This study seeks to generate safety and efficacy data of B/F/TAF FDC in this population by enrolling treatment naïve patients. The comparator regimen contains DTG and F/TDF, a fully suppressive regimen. Potential risks associated with all classes of ARVs include immune reconstitution syndrome, lipodystrophy, and lactic acidosis with steatosis. The risk of class effects is considered to be low. Potential benefits may include provision of a new ARV therapy to patient population that may have fewer side effects than alternative therapies. Other potential benefits include provisions of fixed dose combination therapy, and the knowledge that patient participation will contribute to the body of knowledge of HIV therapies.

In summary, the risk/benefit for this study is acceptable due to the following considerations:

- Treatment of HBV is indicated and important in all HIV co-infected patients due to accelerated progression of liver disease
- TDF and TAF are approved for the treatment of HBV infection
- B/F/TAF has been proven to be safe, well tolerated and effective in the treatment of HIV-infected patients
- Hepatic flares, defined by an increase in ALT of five-fold above upper limit of normal, are not uncommon early in treatment initiation and will be closely monitored (refer to Section [7.5.4](#))
- Risk of nephrotoxicity, defined as a decreased in eGFR < 50ml/min is considered to be low and will be closely monitored (refer to Section [7.5.5](#))

The benefit-risk assessment for this study is favorable at this time.

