7.2.4. Liver-Related Laboratory Evaluations

Liver-related abnormalities after initial study drug dosing will be examined and summarized using the number and percentage of participants who were reported to have the following laboratory test values for postbaseline measurements (based on central laboratory normal range):

- Aspartate aminotransferase (AST): (a) > 3 × ULN, (b) > 5 × ULN, (c) > 10 × ULN,
 (d) > 20 × ULN
- Alanine aminotransferase (ALT): (a) > 3 × ULN, (b) > 5 × ULN, (c) > 10 × ULN,
 (d) > 20 × ULN
- AST or ALT: (a) > $3 \times ULN$, (b) > $5 \times ULN$, (c) > $10 \times ULN$, (d) > $20 \times ULN$ -
- Total bilirubin: (a) $> 1 \times ULN$, (b) $> 2 \times ULN$
- Alkaline phosphatase (ALP > 1.5 × ULN
- AST or ALT $> 3 \times$ ULN and total bilirubin: (a) $> 1.5 \times$ ULN, (b) $> 2 \times$ ULN
- AST or ALT $> 3 \times ULN$ and total bilirubin $> 2 \times ULN$ and ALP $< 2 \times ULN$

The summary will include data from all postbaseline visits up to 30 days after the last dose of study drug. For individual laboratory tests, participants will be counted once based on the most severe postbaseline value. For both the composite endpoint of AST or ALT and total bilirubin, and the composite endpoint of AST or ALT, total bilirubin, and ALP, participants will be counted once when the criteria are met at the same postbaseline visit date. The denominator is the number of participants in the safety analysis set with nonmissing postbaseline value of the tests in evaluation at the same postbaseline visit date. Participants with AST or ALT > 3 × ULN will also be listed.

In addition, baseline, postbaseline, and change from baseline in AST, ALT, ALP, and total bilirubin will be summarized by treatment group and visit using descriptive statistics.

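### Protocol 7.5.4.1 puts an ALT flare with only bilirubin or only INR at threshold in neither branch; its monitoring clause, its relation to 7.5.3 and the flare definition in 1.6 also need reconciling

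*Protocol*

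**What the plan says.** Protocol Section 7.5.4 defines an on-treatment flare as a confirmed "serum ALT $> 2 \times$ Day 1 value and $>10 \times$ ULN, with or without associated symptoms". SAP Section 7.2.5 uses the same numerical threshold, with baseline in place of Day 1.

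Section 7.5.4.1 first gives steps for every such subject: an early return visit, a clinical assessment, reflex tests and repeat liver parameters. It then splits into two branches.

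- First branch: "with normal or stable total bilirubin and INR relative to Day 1, the subject may remain on study medication". The subject "should be monitored weekly as long as ALT levels return to normal or Day 1 level".
- Second branch: "total bilirubin is confirmed to be 2 x Day 1 value, and INR is 0.5 above Day 1", with both above ULN. The investigator should then consider stopping study drug, and the subject "should be monitored weekly as long as ALT, total bilirubin, and INR values remain elevated or above Day 1 values".

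Section 7.5.3 covers Grade 4 laboratory abnormalities. Appendix 5 grades ALT above 10 x ULN as Grade 4, so every flare under 7.5.4 is also Grade 4. Section 7.5.3 requires permanent discontinuation when the abnormality is confirmed, clinically significant and considered related to study drug.

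Section 1.6 speaks of "Hepatic flares, defined by an increase in ALT of five-fold above upper limit of normal", says these will be closely monitored, and refers the reader to Section 7.5.4.

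**The concern.** Section 7.5.4.1 guides the decision on study drug during a hepatic flare in subjects with HBV co-infection. If its two branches do not cover every combination of bilirubin and INR, sites may handle the same laboratory picture differently. If its follow-up clause is taken literally, the condition for weekly monitoring is the reverse of the one in the next branch. If the general Grade 4 rule and the flare rule give different outcomes for one subject, the site needs to know which governs. If Section 1.6 promises close monitoring at one ALT level under a section that starts at another, the risk/benefit statement does not describe what the protocol does.

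**Working it through.** The plan states no figure to reproduce, so the check sets the passages side by side.

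**Branch coverage.** The inputs are the two branch conditions in Section 7.5.4.1. Take three states for bilirubin (normal; raised but below 2 x Day 1; at least 2 x Day 1 and above ULN). Take three for INR (normal; raised by less than 0.5; at least 0.5 above Day 1 and above ULN). That gives 3 x 3 = 9 combinations for a confirmed flare. The second branch joins its conditions with a conjunction and requires both values above ULN, so both must be at threshold.

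| Bilirubin | INR normal | INR raised, below threshold | INR at threshold |
|---|---|---|---|
| Normal | First branch | Depends on stable | Neither |
| Raised, below threshold | Depends on stable | Depends on stable | Neither |
| At threshold | Neither | Neither | Second branch |

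The protocol does not define stable.

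- If stable means not above Day 1, the three dependent cells fall outside the first branch: 9 - 1 - 1 = 7 combinations in neither branch.
- If any sub-threshold rise counts as stable, those three join the first branch: 9 - 4 - 1 = 4 in neither.

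The four that remain are those with exactly one of the two values at threshold. These are counts of combinations, not of subjects; the documents give no frequencies.

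**Relation to Section 7.5.3.** For a confirmed, clinically significant flare that the investigator considers drug-related, 7.5.3 requires permanent discontinuation. Section 7.5.4.1 lets the subject stay on drug in the first branch and asks the investigator to consider stopping in the second. The two outcomes differ, and no readable sentence ranks the sections.

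**Weekly monitoring.** Four statements can be compared.

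1. First-branch clause: weekly, conditional on ALT returning to normal or to the Day 1 level.
2. The next sentence of that branch: what to do if ALT stays persistently raised during monitoring.
3. Second-branch clause: weekly, conditional on values staying raised.
4. Section 7.5.4.2, off drug: followed until values return to normal or Day 1, for at most 6 months.

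Statements 2 to 4 all suppose follow-up while values are abnormal. Statement 1, read literally, does not.

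**Flare threshold.** Section 1.6 gives 5 x ULN whatever the Day 1 value. Section 7.5.4 gives max(10, 2 x Day 1 ALT), in multiples of ULN. Inclusion criterion 7 allows screening ALT up to 10 x ULN.

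| Day 1 ALT (x ULN) | Section 1.6 | Section 7.5.4, must exceed |
|---|---|---|
| up to 5 | 5 | 10 |
| 6 | 5 | 2 x 6 = 12 |
| 8 | 5 | 2 x 8 = 16 |
| 10 | 5 | 2 x 10 = 20 |

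An ALT above 5 and up to 10 x ULN therefore never meets Section 7.5.4. Appendix 5 grades that band as Grade 3, so Section 7.5.2 covers it. By contrast, the neighbouring bullet in Section 1.6 gives eGFR below 50 mL/min and refers to Section 7.5.5, which uses that same figure. These bullets are evidently meant to match the sections they cite.

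**The case against.** The strongest reply is that no subject is left without direction. The steps ahead of the branches apply to every flare. Sections 7.5.2 and 7.5.3 give Grade 3 and Grade 4 rules, Section 7.5 sends questions to the Medical Monitor, and Section 6.9 lists unacceptable toxicity as a reason to stop. Section 7.5.4.1 is itself worded as recommendation. Section 7.5 also relies on Appendix 4, of which only the heading is readable here, so its content could settle some of this. All of that stands. A reader might infer that an isolated bilirubin or INR rise has no stated action at all; the documents do not support that. What is missing is the drug-continuation and follow-up step within 7.5.4.1. The fallback to 7.5.3 brings in a rule with a different outcome and no stated order of precedence.

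On monitoring, the intent can be guessed from the next sentence, and the two branches cover different subjects, so no one subject receives both clauses. That is fair, but the first branch still conflicts with itself. The conditional could instead be attached to staying on drug; weekly monitoring would then have no stated end.

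On the threshold, Section 1.6 is narrative, and the operative definition in 7.5.4 agrees numerically with SAP 7.2.5. A reader might infer that ALT of 5 to 10 x ULN goes unwatched. It does not: chemistry is drawn at every visit, the Grade 3 rules apply, and SAP 7.2.4 tabulates ALT above 5 x ULN. A reader might also infer that a subject who enters at 8 x ULN is already in a flare under Section 1.6. That section describes an increase early in treatment, so a Day 1 value alone does not qualify.

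**Conclusion.** The point holds as a set of internal inconsistencies in the wording.

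- At least four of nine bilirubin/INR combinations fall in neither branch of Section 7.5.4.1. The figure is seven under the strict reading of stable. The four do not depend on how stable is read, provided that a value at the second-branch threshold is not called normal or stable.
- Sections 7.5.3 and 7.5.4.1 can direct different outcomes for the same Grade 4 ALT, with no order of precedence in the readable text. This is subject to whatever Appendix 4 contains.
- The first branch's weekly-monitoring clause is inverted relative to three other statements in Section 7.5.4.
- Section 1.6 and Section 7.5.4 differ by a factor of at least two in ALT (5 against more than 10 x ULN), and by up to four at a Day 1 ALT of 10 x ULN (20 / 5).

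No primary or secondary endpoint, sample size, power or type I error figure is affected. The consequence is inconsistent handling of a hepatic safety event across sites, so the wording should be corrected.

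**What to change.** Reconcile Protocol Sections 1.6, 7.5.3, 7.5.4 and 7.5.4.1, and check the result against Appendix 4, so that:

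1. every combination of bilirubin and INR in a confirmed flare falls in a branch of 7.5.4.1, with stable defined;
2. the relation of the Grade 4 rule in 7.5.3 to the flare rule in 7.5.4.1 is stated;
3. the two weekly-monitoring clauses state the same kind of condition;
4. Sections 1.6 and 7.5.4 agree on what a flare is. SAP 7.2.5 already shares the 7.5.4 numerical threshold and needs a change only if that threshold moves.

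The clinical team must choose the rules; no threshold or action is proposed here. The cost is a clarifying amendment or a letter to sites, with no new procedures.

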7.5.5. Management of Potential Nephrotoxicity

Estimated glomerular filtration rate (eGFR), according to the Cockcroft-Gault formula for creatinine clearance, will be followed post-baseline during the study. All subjects with estimated eGFR < 50 mL/min must have serum creatinine measured again within 3 calendar days of receipt of results.

At the time of this repeat serum creatinine assessment, Cystatin C will also be measured and the eGFR by CKD-EPI (cystatin C) will be calculated and compared with the baseline measurement.

Any subjects who have an eGFR < 50 mL/min that also experience > 20% reduction in eGFR by CKD-EPI (cystatin C) from baseline or who have other clinical and/or laboratory evidence of acute renal failure will be discussed with the Medical Monitor and potentially discontinue from study drugs.

For subjects with eGFR < 50 mL/min who are not discontinued based on toxicity management procedures above and considered to have stable renal function per Principal Investigator and Medical Monitor, it is not mandatory to repeat eGFR assessments within 3 days.

CKD-EPI (cystatin C) formula adjusted for age and sex:

$$\text{eGFR (mL/min/1.73m}^2\text{)} = 133 \times \min(\text{Scys}/0.8, 1)^{-0.499} \times \max(\text{Scys}/0.8, 1)^{-1.328} \times 0.996^{\text{Age}} [\times 0.932 \text{ if female}]$$

Where Scys is serum cystatin C (mg/L), min (Scys/0.8,1) indicates the minimum of Scys/0.8 or 1, and max (Scys/0.8,1) indicates the maximum of Scys/0.8 or 1.

Once an individual subject has developed any of these renal changes and followed the management guidelines above, it is not necessary to have repeat evaluations if it is determined that it is safe for that subject to continue on treatment with standard follow-up visits as described in the protocol.

7.6. Special Situations Reports

7.6.1. Definitions of Special Situations

Special situation reports include all reports of medication error, abuse, misuse, overdose, reports of adverse events associated with product complaints, and pregnancy reports regardless of an associated AE.

Medication error is any unintentional error in the prescribing, dispensing, or administration of a medicinal product while in the control of the health care provider, subject, or consumer.

Abuse is defined as persistent or sporadic intentional excessive use of a medicinal product by a subject.

Misuse is defined as any intentional and inappropriate use of a medicinal product that is not in accordance with the protocol instructions or the local prescribing information.

An overdose is defined as an accidental or intentional administration of a quantity of a medicinal product given per administration or cumulatively which is above the maximum recommended dose as per protocol or in the product labelling (as it applies to the daily dose of the subject in question). In cases of a discrepancy in drug accountability, overdose will be established only when it is clear that the subject has taken the excess dose(s). Overdose cannot be established when the subject cannot account for the discrepancy except in cases in which the investigator has reason to suspect that the subject has taken the additional dose(s).

Product complaint is defined as complaints arising from potential deviations in the manufacture, packaging, or distribution of the medicinal product.

7.6.2. Instructions for Reporting Special Situations

7.6.2.1. Instructions for Reporting Pregnancies

The investigator should report pregnancies in female study subjects that are identified after initiation of study medication and throughout the study, including the post study drug follow-up period, to Gilead PVE using the pregnancy report form within 24 hours of becoming aware of the pregnancy.

The subject's treatment assignment will be unblinded by the Investigator as described in Protocol Section 5.1.1.

Refer to Section 7.3 and the eCRF completion guidelines for full instructions on the mechanism of pregnancy reporting.

The pregnancy itself is not considered an AE nor is an induced elective abortion to terminate a pregnancy without medical reasons.

Any premature termination of pregnancy (eg, a spontaneous abortion, an induced therapeutic abortion due to complications or other medical reasons) must be reported within 24 hours as an SAE. The underlying medical reason for this procedure should be recorded as the AE term.

A spontaneous abortion is always considered to be an SAE and will be reported as described in Sections 7.3. Furthermore, any SAE occurring as an adverse pregnancy outcome post study must be reported to Gilead PVE.

The subject should receive appropriate monitoring and care until the conclusion of the pregnancy. The outcome should be reported to Gilead PVE using the pregnancy outcome report form. If the end of the pregnancy occurs after the study has been completed, the outcome should be reported directly to Gilead PVE. Gilead PVE contact information is as follows:

Email: PPD and Fax: PPD

Refer to Appendix 6 for Pregnancy Precautions, Definition for Female of Childbearing Potential, and Contraceptive Requirements.

7.6.2.2. Reporting Other Special Situations

All other special situation reports must be reported on the special situations report form and forwarded to Gilead PVE within 24 hours of the investigator becoming aware of the situation. These reports must consist of situations that involve study IMP and/or Gilead concomitant medications, but do not apply to non-Gilead concomitant medications.

Special situations involving non-Gilead concomitant medications do not need to be reported on the special situations report form; however, for special situations that result in AEs due to a non-Gilead concomitant medication, the AE should be reported on the AE form.

Any inappropriate use of concomitant medications prohibited by this protocol should not be reported as “misuse,” but may be more appropriately documented as a protocol deviation.

Refer to Section [7.6.1](#) and the eCRF completion guidelines for full instructions on the mechanism of special situations reporting.

All clinical sequelae in relation to these special situation reports will be reported as AEs or SAEs at the same time using the AE eCRF and/or the SAE report form. Details of the symptoms and signs, clinical management, and outcome will be reported, when available.

8. STATISTICAL CONSIDERATIONS

8.1. Analysis Objectives and Endpoints

8.1.1. Analysis Objectives

The primary objectives of this study are:

- To evaluate the efficacy of FDC B/F/TAF versus a regimen of DTG + F/TDF in HIV-1 and HBV treatment naïve, HIV-1 and HBV co-infected subjects as determined by the achievement of HIV-1 RNA < 50 copies/mL at Week 48
- To evaluate the efficacy of FDC B/F/TAF versus a regimen of DTG + F/TDF in HIV-1 and HBV treatment naïve, HIV-1 and HBV co-infected subjects as determined by the proportion of subjects with plasma HBV DNA < 29 IU/mL at Week 48

The secondary objectives of this study are:

- To evaluate the efficacy of FDC of B/F/TAF versus DTG + F/TDF as determined by the achievement of HIV-1 RNA < 50 copies/mL at Week 96
- To evaluate the efficacy of FDC of B/F/TAF versus DTG + F/TDF as determined by the proportion of subjects with plasma HBV DNA < 29 IU/mL at Week 96
- To evaluate the efficacy of the FDC of B/F/TAF versus DTG + F/TDF as determined by the proportion of subjects with ALT normalization at Weeks 48 and 96
- To evaluate the efficacy of the FDC of B/F/TAF versus DTG + F/TDF as determined by the proportion of subjects with HBsAg loss at Weeks 48 and 96
- To evaluate the safety and tolerability of the two treatment groups through Week 96

8.1.2. Primary Endpoints

The primary efficacy endpoint is the proportion of subjects with HIV-1 RNA < 50 copies/mL at Week 48 as defined by the US FDA-defined snapshot algorithm.

The co-primary efficacy endpoint is the proportion of subjects with plasma HBV DNA < 29 IU/mL at Week 48 as defined by Missing = Failure approach.

